## 8. RESEARCH METHODS

### 8.1. Study Design

This is a retrospective register study employing a matched cohort design. This study design was selected to reflect real world usage by utilizing the high-quality registries in Denmark with detailed information on patients with AD. This allows for retrospective analysis of a large number of patients and gives the possibility for comparing with cohort matched control groups (see details below and in section 9.2): the database includes information about close to 13.000 adult patients with a hospital diagnosis of AD. In addition, the database contains information about the general adult population estimated to 4.2 million in 2019. Hence a retrospective study design is more feasible than a prospective design. By matching adult AD patients on conventional systemic therapy with two comparator cohorts – the general Danish population and dermatologist-verified AD patients not receiving systemic treatment – the study contextualizes adverse event rates and isolates the treatment's effect. The general population cohort provides background incidence rates, and the untreated AD cohort helps distinguish the baseline risk from AD itself versus any additional risk due to systemic therapy. Matching on key factors (e.g., age, sex, and cardiovascular risk factors) further enhances methodological rigor by reducing confounding, making the safety outcome comparisons more reliable and clinically meaningful.

Patients with a diagnosis of AD (Table I) are included using the inclusion and exclusion criteria specified in 9.2. AD patients will be matched with individuals from the general population and patients with AD not treated with a systemic to enable relevant comparisons to further investigate safety data in the AD population.

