**Time period**

The study period runs from January 1st, 1995, through December 31st, 2022. In the main analyses, patients are included if they have been diagnosed with AD by a dermatologist in a hospital setting and received the same conventional systemic therapy twice (Table II).

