**Systemic treatment for AD and other indications (biological therapy and targeted synthetic DMARDs)**

Variable (Exclusion criteria)	Role	Data Source	Operational Definition (ATC Code)	Operational Definition (SKS Code)
Baricitinib	Treatment, exclusion criteria	Registry of Medicinal Products Statistics	L04AF02	BWHP106
Upadacitinib	Treatment, exclusion criteria	Registry of Medicinal Products Statistics	L04AF03	BWHP107
Dupilumab	Treatment, exclusion criteria	Registry of Medicinal Products Statistics	D11AH05	BOHJ18B8

Table III. Outcomes.

Variable (ICD-10 diagnostic code description)	Role	Data Source	Operational Definition (ICD-8 diagnostic code)	Operational Definition (ICD-10 diagnostic code)
Dyslipidemia	AE, sec. outcome	National Patient registry		E78 (pre-defined macro)
Herpes zoster 			053.00–053.9	B02
		MACE 		
Stroke	AE, part of primary outcome (MACE)	National Patient registry	NA	I61, I63, I64
Myocardial Infarction	AE, part of primary	National Patient registry	NA	I21, I22

090177e1a4d83c92Approved\Approved On: 11-Nov-2025 17:27 (GMT)

	outcome (MACE)			
CV death (cause of death) 	AE, part of primary outcome (MACE)	National Patient registry	NA	Cause of Death: ICD10: I20-25, I60-61, I63-64, I69, G45.8-45.9, I71, I74, I11.0, I13.0, I13.2, I50, Z95, I46.1, I65, I66, I67.0, I67.2, I70.
Malignancies				
Malignancies, excluding NMSC	AE, co-primary outcome (Malignancy)	National Patient registry	140-209 (except 173)	C00-C99, expect C44
NMSC	Exclusion criteria	National Patient registry	173	C44
Serious infections 	AE, sec. outcome	National Patient registry	Table V	Table V
Arterial thromboembolisms (AT) Venous thromboembolism Deep vein thrombosis (DVT) and pulmonary embolism (PE) 	AE, sec. outcomes	National Patient registry	DVT: 451 PE: 450.99 AT: 444	DVT: I801, I80.2, I80.3, I80.8, I80.9, I82.2, I82.3, I82.9 PE: I26 AT: I74 And anticoagulation therapy: ATC B01A

Table IV. ICD-8 and ICD-10 for medical history

Variable (ICD-10 diagnostic code description)	Role	Data Source	Operational Definition (ICD-8 diagnostic code)	Operational Definition (ICD-10 diagnostic code)	Operational Definition (Nordic Medico-Statistical Committee (NOMESCO) Classification of Surgical Procedures codes)
Alcohol abuse	medical history	National Patient registry	291, 303	F10.1–10.9 (pre-defined macro)	NA
Heart failure	medical history	National Patient registry	NA	I11.0, I13.0, I42, I50	NA

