CVD Risk Factors					

090177e1a4d83c92ApprovedApproved On: 11-Nov-2025 17:27 (GMT)

History of coronary heart disease 	medical history	National Patient registry	NA	I20-I25	PCI (KFNG00, KFNG02, KFNG02A, KFNG05, KFNG05A, KFNG10, KFNG12, KFNG20, KFNG22, KFNG30, KFNG40, KFNG96, KZFX01) or CABG (KFNA, KFNB, KFNC, KFND, KFNE, KFNF, KFNH, KFNJ, KFNK, KFNW)
Diabetes	medical history	National Patient registry	250	E10-E14 (pre-defined macro)	NA
Dyslipidemia (within the past 5 years)	medical history	National Patient registry	NA	E78 (pre-defined macro)	NA
History of cancer	medical history	National Patient registry	140-209	C00-C96	NA
Hypertension	medical history	National Patient registry	400-404 (pre-defined macro)	I10.x-I15.x (pre-defined macro)	NA
Smoking history	medical history	National Patient registry	NA	Pre-defined macro	NA

Table V. ICD-10 Serious infection (see table III, role for all: AE and Secondary Outcome; Data Source: National Patient Registry)

Serious infections	Operational Definition: ICD-10
CNS infections	A02.21, A06.6, A17.0, A20.3, A27.81, A32.1, A39.0, A80-A89, B00.3, B00.4, B01.0, B01.1, B02.0-B02.2, B05.0, B05.1, B06.0, B26.1, B26.2, B10.01, B37.5, B38.4, B43.1, B45.1, B46.1, B58.29, G00-G08

090177e1a4d83c92\Approved\Approved On: 11-Nov-2025 17:27 (GMT)

Gastrointestinal infections	A00, A01, A02.0, A02.8, A02.9, A03-A05, A06.0, A06.2-A06.4, A07-A09, A21.3, A22.2, A42.1, B05.4, B15-B19, B25.1, B46.2, K35, K37, K57, K61, K62.0, K65.0, K65.9, K67, K75.0, K81.0, K81.8, K81.9
Gynecological infections	N70.0, N70.9, N71.0, N71.9, N72, N73.0, N73.2, N73.3, N75.5, N73.8, N73.9, N74
Heart infections	A32.8, B33.21, B37.6, I00, I01, I30, I32, I33, I38-I41, I43.0
Hepatitis	B16, B17, B18
HIV	B20-B24
Musculoskeletal infections	A02.23, H05.029, M00-M03, M46.2, M46.3, M46.5, M46.6, M60.0, M65.0, M65.1, M71.0, M71.1, M86.0-M86.2, M86.8, M86.9, M90.0, M90.1, M90.2
Opportunistic infections	A02, A07.2, A07.3, A15-A19, A27.0, A31, A32, A40.3, A42-A44, A48.1, A48.1, A60.0, A81.2, B00-B02, B17.9, B25, B27.1, B37-B40, B44, B45, B55, B58, B59, B78, B95.3, G02.0, G02.1, J13, J17.1, J17.2, K23.0, K67.3, K93.0
Pulmonary infections	A48.1, A37, B39-B40, B01.2, B05.2, B25.0, B44, B58.3, B59, B95.3, J10-J22, J85, J86, U04
Sepsis	A02.1, A20.7, A22.7, A24.1, A26.7, A28.2B, A32.7, A40, A41, A42.7, B37.7, R65.0, R65.1, R65.9

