### **Registries utilized in this study:**

The Danish National Patient Registry (DNPR) holds information on inpatient visits (since 1977) and outpatient visits (since 1995), along with data on medical procedures, including hospital-administered biologics and phototherapy. Diagnoses are recorded based on the International Classification of Diseases (ICD-8 from 1977 to 1993 and ICD-10 from 1994 onward). Hospital-administered procedures and treatments are registered using the SKS codes, while surgical procedures have been recorded according to the NOMECCO Classification of Surgical Procedures (NCSP) since 1996.

The Danish Register of Medicinal Product Statistics contains information on all filled prescriptions at community pharmacies from 1995 onwards, using the Anatomical Therapeutic Chemical (ATC) classification system.

The National Cause of Death Registry holds information on the cause and date of death when applicable.

The National Population Registry contains demographic information, including vital status and gender.

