## Matching:

Logistic regression will be used to estimate propensity scores (PS). The logit function may include, among others, age, sex, index date (prescription date of conventional systemic therapy), and the presence of at least one cardiovascular risk factor. However, we intend to use clinical judgment to determine which variables will be added based on standardized differences. For matching, we are considering nearest-neighbor (greedy) matching with a 1:1 to 1:4 ratio—likely with replacement. We intend to use a caliper of  $\pm 0.01$  but have also considered  $0.2 \times \text{SD of logit(PS)}$ . Depending on performance, “optimal” matching could also be considered instead. The model with the best properties will be applied. Alternative

approaches for handling matching and assessing model performance are discussed (among others) here.

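### As printed, Table IV takes hypertension, diabetes and dyslipidemia from hospital records only, so matching to the general population can balance the recorded risk flag while true cardiovascular risk still differs

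*Protocol*

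**What the plan says.** Protocol section 8.3, Table IV, defines hypertension as "I10.x-I15.x (pre-defined macro" and diabetes as "E10-E14 (pre-defined macro" (closing brackets omitted). Dyslipidemia is E78, within five years, also with a macro. Each row names the National Patient Registry as its only data source. No row of Table IV has an ATC (drug) code, and the macros are not described anywhere in the protocol.

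Section 8.4 says that this registry "holds information on inpatient visits (since 1977) and outpatient visits (since 1995"); general-practice diagnoses are not mentioned. The same section lists a second study source, the prescription register, which "contains information on all filled prescriptions at community pharmacies from 1995 onwards".

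Section 8.7 (Matching) says the propensity score may include, alongside age, sex and index date, "the presence of at least one cardiovascular risk factor". The final variables are to be chosen by clinical judgment on standardized differences. Section 8.1 states the purpose: "Matching on key factors (e.g., age, sex, and cardiovascular risk factors) further enhances methodological rigor by reducing confounding".

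On selection, section 8.2 (Time period) says "patients are included if they have been diagnosed with AD by a dermatologist in a hospital setting". Under Representativeness, the untreated-AD comparator is also hospital-diagnosed, while the background comparator represents Danish adults without such a diagnosis.

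**The concern.** A condition that can be recorded only at a hospital contact has unequal opportunity to be recorded when one group is selected through hospital contact and the other is not. Hypertension, diabetes and raised lipids can be managed by prescription without a hospital code. The same flag value may then mean different things in the two groups: an unflagged person in one may be more likely to have the condition than an unflagged person in the other.

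The planned checks cannot show this. Standardized differences are computed on the recorded flag, so they can be near zero while true prevalence differs. The inverse-probability-weighted Cox model, planned as a sensitivity analysis, names no other covariate source and would share the problem. The cardiovascular validity study cited in section 8.4 is, by its title in the reference list, a study of positive predictive value, which does not address missed conditions. Section 8.9 mentions miscoding but not unequal capture.

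At stake is how far the general-population hazard ratios for MACE and mortality, and the matched background rates beside them, can be read as free of cardiovascular confounding.

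**Working it through.** The protocol states no figure on this point, so there is none to reproduce. The check asks how far a true hazard ratio of 1 would move if the comparator were matched to the exposed on recorded status.

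**Inputs.** Capture, true prevalence and the effect of the risk factor on MACE are not in the documents. All are assumed and varied. Specificity is taken as 100%.

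- p1, p0: true prevalence in exposed and general population
- s1, s0: proportion of true cases that are recorded
- RR: rate ratio of the risk factor for MACE

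**Formulas.**

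- Recorded prevalence in the exposed, matched in the comparator: m = p1·s1
- True prevalence among unflagged comparators: q0 = p0(1 − s0)/(1 − p0·s0)
- Apparent HR = [1 + (RR − 1)p1] / [m·RR + (1 − m)(1 + (RR − 1)q0)]

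**One case in full.** Take p1 = p0 = 0.25, s1 = 0.60, s0 = 0.40, RR = 2.5.

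- m = 0.25 × 0.60 = 0.15
- q0 = 0.25 × 0.60 / (1 − 0.10) = 0.15/0.90 = 0.167. Among unflagged exposed patients the figure is 0.25 × 0.40 / (1 − 0.15) = 0.118.
- Numerator: 1 + 1.5 × 0.25 = 1.375
- Denominator: 0.15 × 2.5 + 0.85 × (1 + 1.5 × 0.167) = 0.375 + 1.0625 = 1.4375
- Apparent HR = 1.375/1.4375 = 0.957

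**Range.**

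| True prevalence, exposed / comparator | Capture, exposed / comparator | RR | Apparent HR |
|---|---|---|---|
| 20% / 20% | 50% / 40% | 2.0 | 0.99 |
| 20% / 20% | 40% / 30% | 2.0 | 0.99 |
| 20% / 20% | 60% / 30% | 2.0 | 0.96 |
| 20% / 20% | 60% / 30% | 3.0 | 0.93 |
| 25% / 25% | 60% / 30% | 2.5 | 0.94 |
| 30% / 30% | 60% / 30% | 2.0 | 0.95 |
| 30% / 30% | 60% / 30% | 3.0 | 0.92 |
| 30% / 30% | 70% / 25% | 2.5 | 0.90 |
| 20% / 20% | 30% / 30% | 2.0 | 1.00 |
| 20% / 20% | 30% / 40% | 2.0 | 1.02 (1.015) |
| 30% / 20% | 60% / 30% | 2.0 | 1.00 |
| 30% / 20% | 40% / 30% | 2.0 | 1.04 |
| 30% / 20% | 30% / 30% | 2.0 | 1.06 |

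With equal true prevalence, better capture in the exposed pulls the ratio below 1 by about 1% to 10%. With higher true prevalence in the exposed, under-capture in both groups leaves confounding in the other direction, and the two effects can cancel or net above 1.

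**After the fix.** Assume prescription data raise capture to 90% in the exposed and 85% in the comparator, with RR 2. The apparent HR is then 0.99 at equal prevalence of 20% or 30%, 1.00 at 25% versus 20%, and 1.00 at 30% versus 20%. Residual bias is about 1% or less in these cases.

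**The case against.** **The macro may already contain drug codes.** Its content is not shown, and smoking is defined by a macro alone under the same source cell. The source column is also incomplete elsewhere. Table III lists only the National Patient Registry for thromboembolism yet adds "And anticoagulation therapy: ATC B01A", and it lists the same registry for cardiovascular death, although section 8.4 places cause of death in another register. This stands: hospital-only sourcing is what the table prints, not a proven fact about the analysis. If the macros do include drug codes, the source cells are wrong. Table IV needs an edit either way.

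**The direction is not established.** A reader might infer that the matching makes the drugs look safer. That requires better capture in the treated and true prevalence not materially higher in them. The documents give neither, and the table above shows the bias vanishing or reversing. This stands in full.

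**The scope is narrow.** Untreated-AD comparators are also hospital-diagnosed, so unequal capture should be smaller there, and that is the comparison section 8.1 relies on to separate AD risk from treatment risk. Treated-cohort rates are unaffected. The hazard ratios are tertiary, and section 8.7 says no hypotheses are tested. This limits the importance of the point but does not remove it, because section 8.1 says the matching reduces confounding.

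**The size is small against sampling error.** With about 1000 patients per drug (section 8.2) and MACE at 1.5% a year, one year gives 15 events. With 1:4 matching and no effect, the comparator has 60. The standard error of the log HR is √(1/15 + 1/60) = 0.289, so the 95% interval runs from 0.57 to 1.76. With three years assumed (45 and 180 events) it is 0.72 to 1.39. This is fair. However, more follow-up or pooling of drugs shrinks sampling error, not bias.

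**Prescription data may not equalize capture.** People in regular specialist care may also be prescribed for more often. This stands, and it is why remaining inequality should be stated as a limitation.

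**Conclusion.** The point holds in limited form. On the sources printed in Table IV, balance on the recorded cardiovascular-risk flag does not assure balance in true hypertension, diabetes or dyslipidemia between hospital-selected treated patients and the general population. These conditions enter through the any-risk-factor indicator, because the propensity-score list is left open.

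The consequence is residual confounding in the general-population comparison: the tertiary hazard ratios and the matched comparator rates for MACE and mortality. For one binary factor and the assumed inputs, the bias is modest, roughly 1% to 10%. It is below 1 when capture is better in the treated and true prevalence is equal. It is null or above 1 when the treated truly have more risk factors. The upper end of that size needs a wide capture gap (70% versus 25%) for which the documents give no evidence.

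The change is still worth making before analysis: the planned diagnostics cannot reveal the problem, the limitations section does not disclose it, and a better source is already in the study.

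**What to change.** - In Table IV, define hypertension, diabetes and dyslipidemia as a hospital code OR at least two fills of the corresponding ATC groups (antihypertensives, A10, C10). Use the same look-back before the index date in all three groups.
- State a rule for early index dates. Prescription data start in 1995, as does the study period, so a five-year window (the one Table IV already gives for dyslipidemia), for example, is complete only for index dates from 2000.
- Use these definitions in the propensity score and in the inverse-probability weighting, and report balance on them.
- Describe what each pre-defined macro contains. If the macros already include ATC codes, correct the data-source cells instead.
- In section 8.9, state any remaining unequal capture against the general population as a limitation.

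**Cost.** New wording in Table IV and ATC queries in a register the study already uses. Table III already combines ICD and ATC codes, so the technique is not new to this protocol. The downsides are that some of these drugs have other indications, which the two-fill rule only partly addresses, and that early entrants have a shorter look-back.

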Skin and subcutaneous tissue infections	A36.3, A60, B00.1, B00.2, B00.7, B00.9, B01.8, B01.9, B02.3-B02.9, B05.3-B05.9, B08, B09, B35, B36, L00-L05, L08, K11.3, K11.4, K11.6, K12.2, K06.8, K06.9, L30.3, M72.6
Tuberculosis	A19, K23.0, K67.3, K93.0, M01.1, M49.0, M90.0, N33.0, N74.1, N74.1
URTI	A18.6, A36.8, A36.9, H39.0, H39.1, H60.0-H60.3, H60.9, H61.0, H65.0, H65.1, H65.9, H66.0, H66.4, H66.9, H67.1, H70.0, H70.2, H70.8, H70.9, J01, J02, J06, J36
UTI	A54.0-A54.2, N80, N10, N12, N13.6, N15.1, N15.9, N16.0, N30.0, 30.3, N30.9, N34.0, N34.1, N34.2, N39.0, N41.0, N41.2, N45

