## Events

During the treatment series, an adverse event can be adjudicated to the ongoing treatment. In the intention-to-treatment (ITT) study design, the event can be adjudicated to the treatment initiated at the index date.

If a patient is receiving overlapping treatments, any adverse event occurring during both therapies will be adjudicated to the therapy the patient has been on for the longest duration. Such events are referred to as overlapping events.

In the primary analyses, for overlapping events, the event is assigned to the drug the patient has been on the longest.

Multiple sensitivity analyses will be conducted to address overlapping events:

- The event is assigned to the most recent drug.
- The event is attributed to both drugs.
- The event is attributed to neither drug and the patient is censored.

Serious infections are defined as those requiring hospital admission for more than one day (Table V), and infections with HIV, hepatitis B or C, tuberculosis, or infections resulting in death.

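### Table V's Tuberculosis row lists A19 without A15-A18, although the Events text counts tuberculosis as serious without requiring an admission of more than one day

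*Protocol*

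**What the plan says.** Serious infection is a secondary outcome. Table III of the protocol sends it to Table V for its codes, and section 8.7 plans its rate per 10,000 person-years for each conventional drug and for both comparator groups.

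The definition stands under Events in section 8.7: "Serious infections are defined as those requiring hospital admission for more than one day (Table V), and infections with HIV, hepatitis B or C, tuberculosis", followed by infections resulting in death. There are thus two routes. A Table V infection counts if the admission lasts more than one day. HIV, hepatitis B or C, tuberculosis and fatal infections count without that condition.

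Table V has fourteen rows, three of them headed HIV, Hepatitis and Tuberculosis. The Tuberculosis row reads "A19, K23.0, K67.3, K93.0, M01.1, M49.0, M90.0, N33.0, N74.1, N74.1". The opportunistic infections row includes "A02, A07.2, A07.3, A15-A19, A27.0, A31, A32". Single tuberculosis codes also appear in the CNS row ("A02.21, A06.6, A17.0, A20.3") and the URTI row ("A18.6, A36.8, A36.9").

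**The concern.** The Events text exempts tuberculosis as a disease from the admission condition. The only part of the code list that carries the disease's name omits four of the five ICD-10 tuberculosis categories, A15 to A18. Those categories are in Table V, but under headings to which the admission condition applies.

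A programmer who takes the exempt set from the row named Tuberculosis will therefore apply the admission rule to cases that the text says should not need it. Another programmer, who takes the exempt set from A15-A19 in the opportunistic row, would count them. The protocol does not say which is meant, so the same data could give two different serious-infection counts. Under section 8.6 the sponsor receives only final results and no access to source data or coding, so the choice would be hard to see afterwards.

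**Working it through.** The protocol states no figure to reproduce, and no arithmetic applies beyond counting codes. The check has three steps.

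**1. Which Table V rows cover each tuberculosis code.** Ranges and three-character categories are taken to include their subcodes.

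| Code | Rows of Table V that cover it |
|---|---|
| A15, A16 | Opportunistic only |
| A17 | Opportunistic (A17.0 also CNS) |
| A18 | Opportunistic (A18.6 also URTI) |
| A19 | Opportunistic and Tuberculosis |
| K23.0, K93.0 | Opportunistic and Tuberculosis |
| K67.3 | Opportunistic, Tuberculosis, and gastrointestinal (through K67) |
| M01.1, M90.0 | Tuberculosis and musculoskeletal |
| N74.1 | Tuberculosis and gynecological (through N74) |
| M49.0, N33.0 | Tuberculosis only |

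Of the five categories A15 to A19, the Tuberculosis row holds one.

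**2. Apply the Events rule, with the Tuberculosis row as the exempt set.**

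- A19 or a listed organ code: counted, with or without admission.
- A15-A18, admission of more than one day: counted, through the opportunistic row.
- A15-A18, fatal: counted, as an infection resulting in death.
- A15-A18, non-fatal, no admission of more than one day, but also a code from the Tuberculosis row: counted.
- A15-A18, non-fatal, no such admission and no such code: not counted.

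Only the last case conflicts with the text. Such contacts can be in the data, because section 8.4 says that the patient registry has held outpatient visits since 1995, the first year of the study period. Two outpatients who differ only in carrying A18 rather than A19 would be classified differently.

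**3. Is it reasonable to read the row as the exempt set?** The Hepatitis row (B16, B17, B18) lies wholly inside B15-B19 of the gastrointestinal row. For a single composite outcome it adds no code, so its evident use is to mark infections that escape the admission rule. The HIV and Tuberculosis rows fit the same pattern. The Tuberculosis row also opens with A19, K23.0, K67.3, K93.0, while the opportunistic row contains A15-A19 and ends with the same three K codes. That looks like a range cut to its last member in transcription. Nothing in the protocol gives a reason for leaving out A15-A18.

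**The case against.** The strongest reply is that no sentence ties the exemption to the Tuberculosis row. The Events text names a disease, Table III refers to Table V as a whole, and A15-A19 stands in full elsewhere in that table. An analyst could use that range without breaching the text. The row headings also do not match the exempt diseases exactly: the text says hepatitis B or C, while the Hepatitis row is not limited to those two types, so some selection by disease is needed there anyway. This stands, and it is why the loss is conditional on how the exemption is programmed. It does not remove the inconsistency, because the protocol fixes a code list under the name of the exempt disease and that list disagrees with the text.

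A reader might go further and infer that most outpatient tuberculosis is lost, or put a percentage on it. The documents do not support this. They give neither the share of tuberculosis coded A15-A18 nor the share without a qualifying admission, and any such percentage would be of tuberculosis events, not of the outcome. A reader might also infer that a reported tuberculosis subtotal would be wrong, but none is planned: serious infections are reported as one rate. The repeated N74.1 changes no count.

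**Conclusion.** The code list and the definition disagree, and the point holds as a minor correction. It rests on one assumption, that the row headed Tuberculosis defines the tuberculosis exempt from the admission rule. That is the natural reading but not a stated one. On that reading, the cases left out are non-fatal, coded A15-A18, without an admission of more than one day and without a code from the Tuberculosis row.

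The effect is on one component of one secondary outcome. It is probably small, and it cannot be quantified because the protocol gives no tuberculosis rate. The primary outcomes are not touched. The same list serves the treated and comparator groups, so any shortfall could lower the rate in each of them. The documents do not allow a statement about its effect on the hazard ratios.

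**What to change.** In the Tuberculosis row of Table V, change A19 to A15-A19, in agreement with the opportunistic infections row. Under Events in section 8.7, add one sentence stating that this row defines the tuberculosis that counts without an admission of more than one day. The second N74.1 can be deleted at the same time as a cosmetic correction.

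The cost is one table entry and one sentence. A15-A19 is already in Table V, so no new codes or data are needed. The change should be made before the outcome is programmed.
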